### **6.7 Alternatives**

The study has been designed (see above) to minimize potential risks to participants. This is primarily through designation of a dose shown to be safe in previous SBRT trials and careful patient monitoring. The risk of Nelfinavir is minimal as has been documented for greater than a decade following FDA approval in post-market surveillance. Risks to confidentiality will be minimized by having access to study records available only to the investigators with the exception of the standard clinical records (lab values, dictations, operative notes, etc) which are maintained through the Weinberg Comprehensive Cancer Center.

Standard therapies for metastatic disease include conventional radiotherapy, chemotherapy, or observation. Such treatment may or may not be applicable for patients enrolled in this study. Regardless, patients will be expected to forgo standard chemotherapy or radiotherapy until there is evidence of clinical or radiographic disease progression or until completion of a 4-week post-treatment evaluation.

The amount of radiation administered via protocol therapy will be considered in determining how much additional radiation can be given using conventional external beam fractionation.

### **6.8 Costs**

Patients and/or their insurance companies will be responsible for the cost of all procedures and treatments under this protocol except the study drug nelfinavir. Nelfinavir will be supplied to the participant at no cost.

### **6.9 Compensation**

Patients and/or their insurance companies will be responsible for the cost of all procedures and treatments under this protocol.

## **6.10 Withdrawal from Study**

The reasons for withdrawal from the study include:

- Subject withdraws consent for follow-up.
- Subject is lost to follow-up.
- Study is terminated for any reason.

If participants withdraw from the study, they will be followed for survival data.

## **7. INVESTIGATIONAL AGENT/DEVICE/PROCEDURE INFORMATION**

### **7.1 Investigational Agent**

Nelfinavir is the commercially available agent being used in this study.

### **7.2 Availability**

Nelfinavir will be ordered and obtained from the Johns Hopkins Pharmacy.

### **7.3 Agent Accountability**

Only subjects enrolled in the study may receive Nelfinavir, in accordance with all applicable regulatory requirements. Subjects enrolled on the study will self-administer nelfinavir and keep track of their dosing intake via a study drug administration record. Nelfinavir will only be dispensed to the patient when the treating physician involved in the study provided a written order.

## **8. DOSING DELAYS/DOSE MODIFICATIONS**

There will be no dose modifications.

## **9. CORRELATIVE/SPECIAL STUDIES**

### **9.1 Assessment of Phospho-Akt**

- 9.1.1 A blood sample (plasma and serum) will be obtained by venipuncture into a vacutainer coated with 3.2% sodium citrate anticoagulant before Nelfinavir administration, on the day of SBRT treatment, and optionally at the 1MFU. The samples will be centrifuged within 30 minutes of collection and processed in preparation for phosphor-akt assay then stored at -80°C for future analysis.
- 9.1.2 The study coordinator will transport the specimen to the laboratory of [name]., PhD for storage and processing.
- 9.1.3 Specimen will be labeled by patient case ID to protect patient privacy

### 10. STUDY CALENDAR

Parameter	Pre-Study	NFV^ Cycle #1	SBRT ~	NFV^ Cycle #2	Follow-Up%								
					1M (+/- 5 days)	2M (+/- 7 days)	3M i (+/- 7 days)	6M @, h, i	12M @,i	18M @,i	24M @,i	30M @,i	36M @,i
Informed Consent	X												
Demographics	X												
Med HX & Medication Rev	X				X		X	X	X	X	X	X	X
Physical Exam	X				X		X	X	X	X	X	X	X
Vital Signs	X				X								
Height	X				X								
Weight	X				X								
Perf Status	X		X		X	X	X	X	X	X	X	X	X
CBC w/ Diff a	X f				X		X	X	X	X	X	X	X
Serum Chem b	X f				X		X	X	X	X	X	X	X
Coagulation Profile	X f												
Blood Draw for Phospho-Akt	X f		X		X*								
CT or MRI h (of Involved Site(s) o )	X f				X		X	X	X	X	X	X	X
PET-CT*	X f						X	X		X		X	
CT-Guided Fiducial Placement*	X												
AE Evaluation g	X	X d		X d	X	X	X	X	X	X	X	X	X
B-HCG e	X												

^ Nelfinavir (NFV): to be administered in two cycles (1250 mg BID (orally) for 7 days/cycle). Cycle #1 will conclude the day prior to SBRT. Cycle #2 will initiate the day after completion of SBRT.  
~ SBRT: to be administered in one day. However, if scheduling or safety prevents all lesions from being irradiated within one day, participants will complete Cycle #2 of Nelfinavir then undergo a minimum of 7 days “clear out”. Following this break participants will repeat Cycle #1 of Nelfinavir then receive radiation to the remaining lesions followed by a repeat Cycle #2 of Nelfinavir. This process may not exceed three “rounds” of treatment (NFV1, SBRT, NFV2) and may include repeat imaging and/or blood work. Accordingly, the study calendar will be affected.  
% Follow-up appointments will be scheduled based on date of SBRT completion.  
\* indicates optional  
@ +/- 30 days  
a. Including platelets.  
b. Albumin, Alkaline Phosphatase, Total Bilirubin, Bicarbonate, BUN, Calcium, Chloride, Creatinine, Glucose, Potassium, Total Protein, SGOT [AST], SPGT [ALT], Sodium.  
c. Tumor measurements are to be calculated after all radiographic tests.  
d. Will occur on the last day of Nelfinavir Cycle #1 or on date of SBRT administration and the last day of Nelfinavir Cycle #2. May be conducted via phone.  
e. Serum pregnancy test (women of childbearing potential).  
f. Should occur within 30 days of start of Nelfinavir.

SBRT and Nelfinavir

Protocol Chair: [name]

J12137 (NA\_00069585) - May 19, 2020

g. Follow up AE evaluations may be conducted via phone.
h. Required at 3 and 6 months
i. May be conducted via telephone. All procedures are optional, EXCEPT for interval history and AE evaluations. Study staff will remind subjects of upcoming optional procedures at each telephone or follow-up visit. If obtained locally, staff will request that the results be forwarded for study records.

## 11. MEASUREMENT OF EFFECT

### 11.1 Antitumor Effect-Solid Tumors

For the purposes of this study, patients should be re-evaluated for response 4 weeks after the initial treatment, 12 weeks after treatment, 24 weeks after treatment, and every 24 weeks thereafter.

Response and progression will be evaluated in this study using the new international criteria proposed by the Response Evaluation Criteria in Solid Tumors (RECIST 1.1) Committee (30). Changes in only the largest diameter (unidimensional measurement) of the tumor lesions are used in the RECIST criteria.

### 11.2 Definitions

Evaluable Population: will consist of all patients who have received 28 doses of Nelfinavir treatment preceding SBRT.

Safety Population: Will consist of all subjects who were enrolled and have taken at least one dose of the study medication. This will be used to assess the clinical safety and tolerability of the study.

Evaluable for Objective Response: Only those patients who have measurable disease present at baseline, have completed all fractions of SBRT, and have had their disease re-evaluated will be considered evaluable for response. These patients will have their response classified according to the definitions stated below.

### 11.3 Disease Parameters

Measurable Disease: Measurable lesions are defined as those that can be accurately measured in at least one dimension (longest diameter to be recorded) as  $\geq 10$  mm with diagnostic techniques (CT, PET/CT (all are optional), or MRI). All tumor measurements must be recorded in millimeters (or decimal fractions of centimeters).

Non-Measurable Disease: All other lesions (or sites of disease), including small lesions (longest diameter  $< 10$  mm with diagnostic techniques), are considered non-measurable disease. Bone lesions, leptomeningeal disease, ascites, pleural/pericardial effusions, lymphangitis, inflammatory breast disease, abdominal masses (not followed by CT or MRI), and cystic lesions are all non-measurable.

Target Lesions: Target lesions in this study will be considered oligometastatic sites up to a maximum of 5 lesions per patient. They should be recorded and measured at baseline. Target lesions should be equal to or larger than 10 mm in the smallest cross-sectional diameter on CT or MRI and/or any lesion that shows increase metabolic uptake on PET/CT scans. A sum of the longest diameter (LD) for all target lesions will be calculated and reported as the baseline sum LD. The baseline sum LD will be used as reference by which to characterize the objective tumor response.

Non-Target Lesions: N/A

#### **11.4 Methods for Evaluation of Measurable Disease**

All measurements should be taken and recorded in metric notation using a ruler or calipers. All baseline evaluations should be performed as closely as possible to the beginning of treatment and never more than 4 weeks before the beginning of the treatment.

The same method of assessment and the same technique should be used to characterize each identified and reported lesion at baseline and during follow-up. Imaging-based evaluation is preferred to evaluation by clinical examination when both methods have been used to assess the antitumor effect of a treatment.

Conventional CT, PET/CT (all are optional), and MRI These techniques should be performed with cuts of 10 mm or less in slice thickness contiguously. Spiral CT should be performed using a 5 mm contiguous reconstruction algorithm. This applies to tumors of the chest, abdomen, and pelvis. Head and neck tumors and those of extremities usually require specific protocols.

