#### **11.5 Response Criteria (via RECIST 1.1)**

##### **11.5.1 Evaluation of Target Lesions**

Complete Response (CR): Disappearance of all target lesions

Partial Response (PR): At least a 30% decrease in the sum of the longest diameter (LD) of target lesions, taking as reference the baseline sum LD

Progressive Disease (PD): At least a 20% increase in the sum of the LD of target lesions, taking as reference the smallest sum LD recorded since the treatment started or the appearance of one or more new lesions

Stable Disease (SD): Neither sufficient shrinkage to qualify for PR nor sufficient increase to qualify for PD, taking as reference the smallest sum LD since the treatment started

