### 15.6 Analysis of Secondary Objectives

- For safety analysis, adverse events will be summarized by type and grade.
- Hazard rate estimates and 95% confidence intervals as well as Kaplan-Meier (KM) estimates will be used to summarize survival (OS), progression free survival (PFS), time to locoregional progression (TTLP) and time to distant progression (TTDP), duration of response functions over time. The median OS, PFS, TTLP and TTDP will be reported.
- The efficacy of SBRT combined with Nelfinavir with oligometastatic disease will also be determined by measuring local control of each lesion at 6 month. Each metastatic lesion will be considered a target lesion and independently evaluated for response using RECIST 1.1. The lesion will be coded as being locally controlled if it is considered stable radiographic disease or if there is evidence of a partial or complete response. Local control assessment will start at one month following completion of protocol treatment and continuous assessment will be pursued during the follow-up period. The proportion of the lesions that have a stable or better response will be estimated using generalized estimating equation. The above analyses will also be performed by metastases site (bone, liver and lung).
- Quality of life will be assessed using the Brief Pain Inventory form. An overall score will be calculated pre-treatment and at the time of the 2nd radiologic reassessment. The change in score will be evaluated with a paired t-test.
- The analysis for the correlative study will be done by Western blot. The change of phospho-Akt levels will be correlated to progression-free survival outcome.

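### Progression is a 20% rise over the nadir with no minimum in millimetres, so a 2-mm change on a single 10-mm lesion counts as local failure

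*Combined protocol and SAP*

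**What the plan says.** - **Progression rule (11.5.1).** Progressive disease is "At least a 20% increase in the sum of the LD of target lesions, taking as reference the smallest sum LD recorded" since treatment began, or a new lesion. No increase in millimetres is required, and no other section adds one.
- **Lesion level (15.6).** "Each metastatic lesion will be considered a target lesion and independently evaluated for response using RECIST 1.1". The 20% then applies to one diameter.
- **Entry size (11.3).** "Target lesions should be equal to or larger than 10 mm in the smallest cross-sectional diameter on CT or MRI". Raised PET uptake is an alternative way in, and that PET route carries no size limit. Bone lesions are classed as non-measurable.
- **Imaging (11.4).** For conventional CT, PET/CT and MRI: "These techniques should be performed with cuts of 10 mm or less in slice thickness contiguously". The next sentence adds: "Spiral CT should be performed using a 5 mm contiguous reconstruction algorithm". The same technique is to be used at baseline and follow-up.
- **Scans (6.3 and the section 10 calendar).** CT or MRI is required at months 3 and 6. Imaging at other follow-up visits is optional.
- **Review (11.5.6).** A co-investigator radiologist reviews responses. No confirmatory scan is called for.
- **Primary endpoint (15.5).** FFLP runs to documented local progression, with no measurement threshold. Sections 6.3, 11.1, 11.5 and 15.6 name RECIST 1.1, whose text is not reproduced.

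**The concern.** A purely relative threshold shrinks with the lesion. For small lesions it comes close to the size of ordinary reading error. Measuring from the nadir makes this one-sided: one low reading lowers the reference for every later scan, and no confirmatory scan is required to undo a false call. Errors of this kind turn stable lesions into local failures, which lowers 6-month lesion control. If the same rule is used for FFLP, it lowers the primary endpoint too, in a trial that has to separate 90% from 70% with 42 patients.

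**Working it through.** **Step 1. What the rule requires.** Rise needed = 0.20 × reference diameter.

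- 8 mm (possible only by the PET route): 1.6 mm
- 10 mm: 2 mm
- 15 mm: 3 mm
- 20 mm: 4 mm
- 25 mm: 5 mm

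At patient level the 20% applies to the sum. Five 10-mm lesions sum to 50 mm and need a 10-mm rise. The 2-mm case is therefore confined to lesion-level calls and single-lesion patients. A 5-mm minimum binds only when the reference is below 25 mm.

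**Step 2. Assumptions for a truly stable lesion.** The documents give no measurement error, so it is assumed: independent normal reading errors with SD σ = 0.5, 1.0 or 1.5 mm. Each lesion has a baseline reading and the two required scans. It is called progressed if a reading is at least 1.2 × the smallest earlier reading. To respect 11.3, lesions are kept only if the baseline reading is at least 10 mm.

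**Step 3. Hand check of one comparison, before the entry condition.** P(month 3 ≥ 1.2 × baseline) = Φ(−0.2L / (σ√(1 + 1.2²))). For L = 10 and σ = 1.0 this is Φ(−2/1.562) = Φ(−1.28) = 10.0%. Simulation gives the same.

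**Step 4. False progression by month 6 (4,000,000 draws, readings not rounded).**

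| True diameter | Rule | σ = 0.5 | σ = 1.0 | σ = 1.5 |
|---|---|---|---|---|
| 10 mm | 20% only | 0.5% | 11% | 23% |
| 10 mm | 20% and 5 mm | 0% | 0.02% | 0.9% |
| 20 mm | 20% only | 0% | 1.5% | 11% |

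The nadir drives the 10-mm result. At σ = 1.0, only 0.5% are called at month 3, against 10% at month 6, mostly after a low month-3 reading.

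**Step 5. Sensitivity to the assumptions (10-mm lesion, 20% only, no entry condition).**

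- Two scans: about 1.5%, 23% and 42%. This is nearer the position of a lesion admitted by PET.
- Two scans, readings rounded to whole millimetres: 7%, 33% and 48%.
- Three scans, if the optional month-1 scan is also used: 3%, 37% and 60%.

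The entry condition lowers the figures because it selects lesions whose baseline happened to read high.

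**The case against.** **RECIST 1.1 is adopted by name.** It may contain an absolute minimum, and 11.5.1 may be an incomplete transcription. That cannot be checked from the documents. Section 11.5.1 writes out its own operative rule, and anyone applying it as written finds no minimum. If the source has one, the change only makes the text agree with it.

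**Slice thickness.** A reader might infer that 10-mm cuts alone make stable small lesions appear to grow. The documents do not support this. Cuts are contiguous, so the widest section always lies inside some slice, and spiral CT is already set at 5 mm. A model of thin planes 10 mm apart can only understate a sphere's diameter, so a 10-mm sphere would never read 10 mm at baseline and would not qualify on size. Partial-volume error is real, but the documents give nothing from which to size it. The estimates above rest on reading error alone.

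**Primary endpoint.** A reader might also infer a definite loss of power. If 2%, 5% or 10% of truly controlled patients were miscalled, a 90% FFLP would read as 88.2%, 85.5% or 81.0% (0.90 × 0.98, 0.95, 0.90). Nothing in the documents fixes that fraction. Section 15.5 states no threshold, the patient-level rule uses the sum, and lesions up to 5 cm are eligible with no size distribution given.

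**A minimum has its own bias.** This stands. A slice interval is not caliper precision, so 5 mm is a choice rather than a derived value. A lesion growing from 10 to 14.9 mm has 1.49³ = 3.3 times the volume and would still count as controlled. Month-12 imaging is optional, so such growth may be recorded only after the 6-month landmark, which raises FFLP in a single-arm trial.

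**Conclusion.** The concern holds for lesion-level calls and single-lesion patients. As written, 2 mm on a 10-mm lesion is progression. Under assumed reading SDs of 0.5 to 1.5 mm, the chance of calling a stable, size-eligible 10-mm lesion progressed by month 6 runs from about 0.5% to 23%. For a 20-mm lesion it runs from 0% to 11%. A 5-mm minimum brings the 10-mm figure below 1% throughout. The result depends on the assumed SD and on independent normal errors. Radiologist review and the same-technique rule may reduce the error, but neither sets a threshold. The effect on FFLP is an inference, not a demonstrated loss. The point deserves a wording change and does not undermine the design.

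**What to change.** 1. **11.5.1, and lesion calls in 15.6:** require both a 20% rise and an absolute increase of at least 5 mm over the nadir. Apply this to the sum at patient level and to the lesion's own diameter at lesion level.
2. **15.5:** state that this rule defines local progression for FFLP.
3. **11.4:** extend the 5-mm limit already set for spiral CT to the other CT and MRI scans used at baseline, month 3 and month 6.
4. **15.5 and 15.6:** report 6-month FFLP and lesion control under the 20%-only rule as a sensitivity analysis, so that the effect of the minimum is visible in both directions.

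The cost is wording, one extra analysis and a tighter limit on non-spiral CT and MRI; no visits are added. The price is later recording of some true small progressions, for example from 10 mm to under 15 mm, possibly after the 6-month landmark. Item 4 is there to show that effect.

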#### **11.5 Response Criteria (via RECIST 1.1)**

##### **11.5.1 Evaluation of Target Lesions**

Complete Response (CR): Disappearance of all target lesions

Partial Response (PR): At least a 30% decrease in the sum of the longest diameter (LD) of target lesions, taking as reference the baseline sum LD

Progressive Disease (PD): At least a 20% increase in the sum of the LD of target lesions, taking as reference the smallest sum LD recorded since the treatment started or the appearance of one or more new lesions

Stable Disease (SD): Neither sufficient shrinkage to qualify for PR nor sufficient increase to qualify for PD, taking as reference the smallest sum LD since the treatment started

##### **11.5.2 Evaluation of Non-Target Lesions**

N/A

##### **11.5.3 Evaluation of Best Overall Response**

The best overall response is the best response recorded from the start of the treatment until disease progression/recurrence (taking as reference for progressive disease the smallest measurements recorded since the treatment started). Best overall response will be based on the overall response of the target lesions.

#### 11.5.4 Duration of Response

Response will be defined as evidence of CR, PR, or stable disease. The duration of response will be measured from the start of treatment until the criteria for progression are met.

Duration of CR or PR: The duration of CR or PR will be recorded from the time measurement criteria are met for CR or PR (whichever is first recorded) until the first date that current or progressive disease is objectively documented (taking as reference for progressive disease the smallest measurements recorded since the treatment started).

Duration of Stable Disease: Stable disease is measured from the start of the treatment until the criteria for progression are met, taking as reference the smallest measurements recorded since the treatment started.

#### 11.5.5 Clinical Response Parameters

**Time to Local Progression (TTLP)** is defined as the elapsed time from the start of treatment to the date of documented local progression or death, whichever happens earliest.

**Progression-Free Survival (PFS)** is defined as the time from starting treatment to the time of first documented tumor progression or death due to any cause, whichever occurs first. Death is considered as an event here. For subjects whose disease does not progress or who do not die, PFS will be censored at the time of the last visit.

**Time to Progression (TTP)** is defined as the time from starting treatment to the time of first documented tumor progression. Subjects who do not progress will be censored at the time of the last contact. In addition, death from any cause will also be censored.

**Overall Survival (OS)** is defined as the time from starting treatment until death due to any cause. For subjects who do not die, time to death will be censored at the time of last contact.

**Locoregional Control (LRC)** is defined as the time from starting treatment until local and/or regional relapse is documented

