### 6.3 Follow-Up Procedures

Subsequent to SBRT, patients will be followed clinically for toxicity and interval history at Months 1, 2, 3, 6, 12, and every 6 months thereafter until 3 years post SBRT. A detailed medical and physical examination will be performed at 4 weeks, 3 months, 6 months and 1 year post SBRT. The following procedures are optional at Months 1, 3, 6 and every 6 months through 3 years post SBRT:

- A complete blood count (CBC) and comprehensive chemistry panel
- CT scan or MRI including the treated site (Note: this is required at Months 3 and 6 for the reason noted below)
- Physical Exam and ECOG Performance Status

PET-CT will be recommended at 3 months, 6 months, and annually thereafter however all are optional.

CT scans at 3 and 6 months will be used to determine radiographic response based on RECIST 1.1 criteria.

All follow-ups may be conducted by telephone for patient convenience. Study staff will request any of the optional procedures noted above that were performed by local physicians to be forwarded for study records.

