#### **15.1.2 Secondary Objectives**

- To describe the toxicity of SBRT combined with Nelfinavir delivered for the population enrolled using grading with CTCAE v. 4.0
- To determine the local control at 6 months after SBRT is delivered to a dose of 15 Gy in 1 fraction (per lesion rate) combined with Nelfinavir in patients with oligometastatic disease.
- To assess long-term clinical outcomes of this patient population after completion of SBRT and Nelfinavir by measuring progression-free survival and overall survival. Progression-free survival will be measured from time of enrollment to date of disease progression or death. Patients who are lost to follow-up will be censored for determination of progression-free survival on the date of their last evaluation. Overall survival is defined as time from enrollment to death due to any cause.
- To assess quality of life following completion of SBRT and Nelfinavir using pre- and post-SBRT completion of the Brief Pain Inventory form which will be filled out by the patient at the treatment response intervals outlined above.

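### PFS is censored at the last visit, which may be a telephone call, so unscanned time after month 6 counts as progression-free and can inflate late PFS

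*Combined protocol and SAP*

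**What the plan says.** - **PFS, Section 11.5.5:** "For subjects whose disease does not progress or who do not die, PFS will be censored at the time of the last visit".
- **PFS, Section 15.1.2:** "Patients who are lost to follow-up will be censored for determination of progression-free survival on the date of their last evaluation". This covers only patients lost to follow-up, and the term evaluation is not defined.
- **TTP, Section 11.5.5:** "Subjects who do not progress will be censored at the time of the last contact".
- **What a visit may be:** Section 6.3 says "All follow-ups may be conducted by telephone for patient convenience". Footnote i of the Section 10 calendar treats a call as a kind of visit: "Study staff will remind subjects of upcoming optional procedures at each telephone or follow-up visit". It applies from month 3 and adds: "All procedures are optional, EXCEPT for interval history and AE evaluations". Footnote g says: "Follow up AE evaluations may be conducted via phone".
- **Imaging:** Section 6.3 and footnote h require CT or MRI at months 3 and 6. Scans from month 12 to month 36 are on the calendar but optional. Section 11.1 says patients should be re-evaluated every 24 weeks after week 24.
- **Analysis:** Section 15.6 plans Kaplan-Meier curves and median PFS, and does not say which censoring rule applies.

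**The concern.** Section 11.5.1 defines progression as a 20% rise in the sum of longest diameters or the appearance of new lesions. A telephone call can establish neither. Under the last-visit rule, a patient last scanned at month 6 and telephoned until month 36 contributes 36 - 6 = 30 months of progression-free time with no scan that could have shown otherwise.

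At stake is the later part of the PFS curve, which is one of the two measures Section 15.1.2 names for long-term outcome. In a single-arm trial there is no control arm in which the same fault would cancel. Because 15.1.2 words the rule differently for patients lost to follow-up, two analysts could also draw different curves from the same data.

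**Working it through.** **Anchor from the plan.** No PFS figure is stated, so there is none to reproduce. Section 15.2 gives local-progression hazards of 0.06 and 0.02 per month. They follow from its 6-month rates: -ln(0.70)/6 = 0.059 and -ln(0.90)/6 = 0.018, a reduction of about 70%, as stated.

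**Assumptions, none of them in the documents.** Progression hazard h is 0.02, 0.06 or 0.10 per month (PFS also includes distant progression). Death hazard is 0 or 0.02 per month. All scans to month 6 are done. Uptake at months 12 to 36 is 100%, 75% or 50%. Contact is complete, and progression is found only by scan.

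**Closed form, no deaths, a share u of patients never rescanned after month 6.**
- Full imaging: S(24) = exp(-24h).
- Last-contact censoring: unscanned patients stay at risk and cannot have an event, so S(24) = exp(-6h) × [u + (1 - u) exp(-18h)].
- Last-imaging censoring: they leave the risk set at month 6, so S(24) = exp(-6h) × exp(-18h) = exp(-24h).

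With h = 0.06 and u = 0.5: exp(-0.36) = 0.698 and exp(-1.08) = 0.340. Last contact gives 0.698 × (0.5 + 0.170) = 46.7%. Last imaging and full imaging both give exp(-1.44) = 23.7%. Simulation with 40,000 patients gave 47.0%, 24.0% and 23.9%.

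**Simulated 24-month PFS, same patients never rescanned, 50% unscanned (gap at 25% in the last column).**

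| Progression hazard | Death hazard | Last contact | Last imaging | Full imaging | Gap, 50% | Gap, 25% |
|---|---|---|---|---|---|---|
| 0.02 | 0 | 75.0% | 61.5% | 61.6% | 13.5 | 6.6 |
| 0.06 | 0 | 47.0% | 24.0% | 23.9% | 23.0 | 11.1 |
| 0.10 | 0 | 32.0% | 8.9% | 8.8% | 23.1 | 11.3 |
| 0.02 | 0.02 | 46.9% | 34.7% | 38.4% | 12.2 | 5.6 |
| 0.06 | 0.02 | 28.7% | 16.4% | 14.8% | 12.3 | 6.6 |
| 0.10 | 0.02 | 19.8% | 8.6% | 5.7% | 11.2 | 5.5 |

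The gap between the rules at 24 months is 5.5 to 23.1 points. At 12 months it is 2.3 to 12.6 points.

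**Scans missed at random visits.** The gap is 0.1 to 2.5 points at 24 months and 0 to 0.4 at 12 months. Both rules then overstate PFS because detection is late: with h = 0.06, no deaths and 50% uptake, they give 35.2% and 32.7% against 24.0% with full imaging. With 100% uptake the gap is zero. Last contact was never below last imaging.

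**Last imaging is not exact once deaths occur.** With both hazards 0.02 and half unscanned, it reads 34.7% against 38.4%, because late deaths count while survivors are removed at month 6. At higher progression hazards it ends slightly above full imaging (16.4% against 14.8%).

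**Median PFS.** Take a median time to progression of 9 months, 40% dead at 24 months, and the same patients unscanned. The median is 10.7 months with full imaging, and 10.7 (25% unscanned) or 10.9 (50%) under last contact. The curve crosses 50% before the month-12 scan, so missed later scans hide little. Last-imaging censoring with no rule for late deaths lowered it to 9.5 and 8.3; the size of that fall depends on how those deaths are treated. With slower events the median does move: at h = 0.06, no deaths and 50% unscanned, 12-month PFS is 59.4% under last contact and 49.1% with full imaging, so only the latter has crossed 50%.

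**The case against.** The strongest reply is that the documents expect more imaging than the required minimum. CT or MRI is on the calendar from month 12 to month 36, Section 11.1 asks for re-evaluation every 24 weeks, staff remind patients and request local results, and interval history is mandatory. If uptake is high, or gaps are scattered, the rule hardly matters. PFS is also secondary and descriptive, with no test or threshold attached, and the named summary is the median. All of this stands. It limits the size but does not remove the fault, since none of it obliges a scan after month 6 and 11.5.5 dates censoring by the visit.

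The reply is also right that last-imaging censoring alone is an incomplete remedy, as the results with deaths show.

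A reader might infer that 11.5.5 and 15.1.2 contradict each other for every patient and that 15.1.2 is the sound rule. The documents do not support that. Section 15.1.2 speaks only of patients lost to follow-up; for other event-free patients 11.5.5 is the only rule. Its last evaluation could itself be a telephone AE evaluation, so the two dates may coincide.

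**Conclusion.** The point holds in this form: the last-visit rule permits unscanned time to count as progression-free and can inflate PFS after month 6. Under the assumed hazards, with 25-50% unscanned, the two rules differ at 24 months by about 0-3 points if scans are missed at random and about 6-23 points if the same patients are never rescanned. The direction is firm. The size is not, because it rests on uptake and hazards the documents do not give, and median PFS may move little.

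Three stronger conclusions might be drawn and are not supported:
- That PFS will be inflated by the upper figure. This needs half the patients never rescanned yet always contacted, with no progression found by history or local scans.
- That the primary result is compromised. The 6-month FFLP falls within the period of required imaging, so it is largely unaffected.
- That a planned TTP result is biased. TTP has the same weakness in its definition, but Section 15.6 does not list it among the analyses.

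**What to change.** Put one PFS rule in Sections 11.5.5 and 15.1.2, and refer to it from 15.6:

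1. Censor patients who are alive without documented progression at the date of their last adequate tumour imaging, with adequate imaging defined. Apply this also to patients lost to follow-up, in place of the undefined last evaluation.
2. State how deaths and progressions that follow missed assessments are handled: counted at the event date, or censored at the last adequate imaging. Neither choice is free of bias, so name the main one in advance and report the other.
3. Report last-contact censoring as a sensitivity analysis, with the number of patients imaged at each time point after month 6.
4. Use the same censoring date for TTP if it is reported. Keep last contact for OS.

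The same edit can settle a separate mismatch: PFS starts at the start of treatment in 11.5.5 but at enrollment in 15.1.2.

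The cost is wording only. No added visits, scans or patients are needed. Late PFS will look less favourable and be less precise. The rule does not cure delayed detection when scans are skipped intermittently, and the report should say so.
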